1.3 Regorafenib

Regorafenib has potent preclinical antitumor activity and long-lasting anti-angiogenic activity as measured by dynamic contrast enhanced (DCE) – magnetic resonance imaging (MRI) (1). Regorafenib is a small molecule inhibitor of multiple membrane-bound and intracellular kinases involved in normal cellular functions and in pathologic processes such as oncogenesis, tumor angiogenesis, and maintenance of the tumor microenvironment. In *in vitro* biochemical or cellular assays, Regorafenib or its major human active metabolites M-2 and M-5 inhibited the activity of RET, VEGFR1, VEGFR2, VEGFR3, KIT, PDGFR-alpha, PDGFR-beta, FGFR1, FGFR2, TIE2, DDR2, Trk2A, Eph2A, RAF-1, BRAF, BRAFV600E, SAPK2, PTK5, and Ab1 at concentrations of Regorafenib that have been achieved clinically. In *in vivo* models, Regorafenib demonstrated anti-angiogenic activity in a rat tumor model, and inhibition of tumor growth as well as anti-metastatic activity in several mouse xenograft models including some for human colorectal carcinoma.

1.3.1 Preclinical

In vivo, Regorafenib exhibited anti-angiogenic and anti-proliferative effects in human colon and breast xenografts as demonstrated by a reduction in microvessel area, reduced Ki-67 staining, and reduced pERK1/2 staining in tissue sections from tumor xenografts, and dose-dependent inhibition of growth in multiple xenograft models (breast, colon, renal, NSCLC, melanoma, pancreatic, thyroid, ovarian). (1) Immunohistochemical ex-vivo studies with a phospho-specific monoclonal anti-ERK 1 / 2 antibody demonstrated inhibition of the MAPK pathway five days after treatment with Regorafenib in 2 of 3 tumor models examined (MDA-MB 231 and BxPC-3), but not in NSCLC (H460).

In addition, all tested human tumor xenografts (MDA-MB-231, H460, BxPC-3 and Colo-205) demonstrated a significant reduction in new blood vessels by histomorphometry as detected in tumor samples using a murine CD31 antibody. (1) These data suggest that Regorafenib can target the tumor cell MAPK pathway (tumor cell survival) and tumor vasculature in some but not all tumors.

1.3.2 Clinical experience

Two phase III global randomized studies have evaluated the efficacy of Regorafenib. The CORRECT (Patients with metastatic colorectal cancer treated with Regorafenib or placebo after failure of standard therapy) trial is an international, multicenter, randomized, double-blind, placebo-controlled study that enrolled 760 patients with mCRC whose disease has progressed after approved standard therapies. Metastatic colorectal cancer patients were randomized to Regorafenib plus best supportive care (BSC) or placebo plus BSC. Treatment cycles consisted of 160 mg of Regorafenib (or matching placebo) once daily for three weeks on / one week off plus BSC. The primary endpoint of this trial was overall survival. Secondary endpoints included progression-free survival, objective tumor response rate and disease control rate. The safety and tolerability of the two treatment groups were also compared.

At a preplanned second interim analysis, there was a statistically significant survival benefit for Regorafenib. The estimated hazard ratio for overall survival was 0.773 (95% confidence interval [CI], 0.635 to 0.941; 1-sided $p = .0051$). Patients treated with Regorafenib had a median overall survival of 6.4 months, compared with 5.0 months for placebo — a 29% increase in survival. In addition to improved overall survival, progression-free survival was superior; median progression-free survival was 1.9 months (95% CI, 1.88 to 2.17) for Regorafenib and 1.7 months (95% CI, 1.68 to 1.74) for placebo. The estimated hazard ratio for progression-free survival was 0.493 (95% CI, 0.418 to 0.581; 1-sided $p < .000001$). There was a substantial difference in disease control rate in the Regorafenib and placebo groups (44% vs. 15%; $p < .000001$). Regorafenib demonstrated comparable efficacy benefits across patient subgroups analyzed including age, number of mets, number of lines of prior therapy, and kras status.

The most frequent grade 3+ adverse events in the Regorafenib group were hand–foot skin reaction (17%), fatigue (15%), diarrhea (8%), hyperbilirubinemia (8%), and hypertension (7%). The efficacy and safety from the CORRECT study supported FDA approval in September 2012.

The efficacy and safety of Regorafenib were examined in the Phase III GRID trial in patients with gastrointestinal stromal tumors (GISTS) who had exhausted all other treatment options. The study involved 199 patients with metastatic and/or unresectable GIST that had become resistant to imatinib and sunitinib. Patients were randomized 2:1 to Regorafenib (160 mg orally once daily on a 3 weeks on/1 week off cycle) or placebo, plus best supportive care.

The results showed that treatment with Regorafenib led to a statistically significant 3.9-month improvement in progression-free survival (PFS), compared with placebo (4.8 months vs. 0.9 months; hazard ratio [HR] = 0.27; $p < .0001$). Overall survival was statistically similar between groups as expected due to a trial design that allowed crossover to Regorafenib for disease progression (85% for placebo and 31% Regorafenib randomized patients). The median survival period without tumor growth among patients on Regorafenib was 4.8 months while for the control group on placebo it was less than a month. The overall disease control rate combining partial responses with durable stable disease for at least 12 weeks was 53% with Regorafenib compared with 9% in the control group. The most common grade ≥ 3 adverse events associated with Regorafenib were hand–foot skin reaction (56.1%), hypertension (48.5%), and diarrhea (40.9%). The efficacy and safety of the GRID study data supported FDA approval February 2013.

However, Regorafenib dose reductions are common in colorectal cancer and GIST patients, and advanced urothelial carcinoma patients are ~5-10 years older (by median age). Dose reductions or interruptions appear common (43.8%) in off-study patients despite being initiated on a dose lower (120 mg daily) than the recommended initial dose (33.3%) (57). In the aforementioned pivotal phase III trials in colorectal and GISTs, dose interruptions are reductions occurred quite commonly. In the colorectal cancer trial, 333 (67%) and 304 patients (61%) in the Regorafenib group had an adverse event leading to dose modification or dose interruptions. In the GIST trial, dose modifications occurred in 95/132 patients (72.0%) on Regorafenib.

2. Study objectives

2.1 Primary Objective

Progression-free survival (PFS) at 6 months (PFS6)

2.2 Secondary Objectives

- Measurable disease response rate (RECIST)
- Overall survival
- Comparison of observed PFS6 with expected/estimated PFS6 by nomogram
- Toxicities

2.3 Exploratory objectives

- Association of tumor IHC for Tie2 and VEGFR2 with PFS
- Association of Gene expression in tumor tissue using Nanostring technology

3. Investigator[s] and other study participants

Principal Investigator

[name]
UAB Comprehensive Cancer Center
[name]
[name]
[contact]
[contact]
Email address: [contact]

Co-Investigators

[name]
[name]
[name]

[name], MD is a Professor in Department of Medicine, division of Hematology and Oncology at University of Alabama at Birmingham (UAB) and a Scientist at UAB Comprehensive Cancer Center (UABCCC). [name] is the director of urologic oncology at Wayne State University Karmanos Cancer Institute, and has extensively accrued in urothelial cancer trials and published multiple studies. [name], MD is an

[figure not shown]
Assistant Professor in the Department of Medicine, Division of Hematology and Oncology at UAB. He will see patients at Kirklin clinic along with [name]. [name] is a faculty urologic medical oncology physician with Cleveland Clinic where he is active with clinical trials and patient care.

4. Study design

This is a 3-center one-stage phase II trial conducted at the UAB Comprehensive Cancer Center (Birmingham, AL), Wayne State Karmanos Cancer Institute (Detroit, MI), and the Cleveland Clinic (Cleveland, OH). The trial will be managed by the Clinical Trial Network Monitoring Office (CTNMO) housed at the UAB Comprehensive Cancer Center. Progression free survival at 6 months is the primary end- point and the trial will enroll 35 patients. The eligible population includes patients with advanced urothelial cell carcinoma who have progressive disease after 1-3 prior chemotherapy regimens. Regorafenib is taken orally and is administered daily for the first 21 days of each 28 day cycle. The dose of Regorafenib is 120 mg once daily for the first cycle, which will be escalated to 160 mg once daily from the second cycle if no Regorafenib-related toxicities greater than grade 1 occur. Each 28 day cycle will be repeated until disease progression, intolerable toxicities, or patient decision with no limit on number of cycles allowed. Radiological evaluations are performed at each institution using RECIST 1.1 criteria every 2 cycles (8 weeks) or earlier if clinically indicated. Progression free-survival will be defined as the time to first occurrence of any of the following:

1. Clinical symptoms and signs of progression of disease,
2. Progression in measurable disease as defined by RECIST 1.1 criteria,
3. Death.

Trial schema

5. Study Population

5.1 Eligibility criteria

5.1.1 Inclusion criteria

Each patient must meet all of the following inclusion criteria to be enrolled in the study:

- Patients must have pathologically or cytologically proven TCC of the urothelium
- Progressive disease after 1-3 prior chemotherapy regimens (perioperative chemotherapy within 12 months will be considered one regimen)
- Prior regimen must be within 6 months of registration
- Measurable disease by RECIST 1.1
- ECOG Performance status 0 - 2

- Patients with metastatic (lymph node or distant metastasis, i.e. N+ or M1) or locally advanced unresectable (T4b) TCC
- Age 19 years or older
- Life expectancy of at least 12 weeks (3 months).
- Subjects must be able to understand and be willing to sign the written informed consent form. A signed informed consent form must be appropriately obtained prior to the conduct of any trial-specific procedure.
- Adequate bone marrow, liver and renal function as assessed by the following laboratory requirements:
 - Total bilirubin $\leq 1.5 \times$ the upper limits of normal (ULN)
 - Alanine aminotransferase (ALT) and aspartate amino-transferase (AST) $\leq 2.5 \times$ ULN ($\leq 5 \times$ ULN for subjects with liver involvement of their cancer)
 - Alkaline phosphatase limit $\leq 2.5 \times$ ULN ($\leq 5 \times$ ULN for subjects with liver involvement of their cancer)
 - Serum creatinine $\leq 1.5 \times$ the ULN
 - International normalized ratio (INR) $\leq 1.5 \times$ ULN and partial thromboplastin time (PTT) or activated partial thromboplastin time (aPTT) $\leq 1.5 \times$ ULN **unless receiving treatment with therapeutic anticoagulation.**
(Subjects who are prophylactically treated with an agent such as warfarin or heparin will be allowed to participate provided that no prior evidence of underlying abnormality in coagulation parameters exists. Close monitoring of at least weekly evaluations will be performed until INR/PTT is stable based on a measurement that is pre-dose as defined by the local standard of care. (See Section 3.3))
 - Platelet count $> 100000 /mm^3$, hemoglobin (Hb) $> 8 \text{ g/dL}$, absolute neutrophil count (ANC) $1500/mm^3$. The patient cannot be transfused in order to meet study entry criteria
- Women of childbearing potential must have a negative pregnancy test (urine or serum) performed within 7 days prior to the start of study drug. Post-menopausal women (defined as no menses for at least 1 year) and surgically sterilized women are not required to undergo a pregnancy test. The definition of adequate contraception will be based on the judgment of the investigator.
- Subjects (men and women) of childbearing potential must agree to use adequate contraception beginning at the signing of the ICF until at least 3 months after the last dose of study drug. The definition of adequate contraception will be based on the judgment of the principal investigator or a designated associate.
- Subject must be able to swallow and retain oral medication.

Commented [YW1]: The definition of this Inclusion criteria does not change.

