However, when starting at the US FDA approved dose of 160 mg once daily for colon cancer and GIST, Regorafenib dose reductions owing to toxicities are common and may be necessary in up to 60-70% of patients (57). The most common adverse events (AEs) of any grade that occurred in $\geq 10\%$ of patients include fatigue, decreased appetite and food intake, hand-foot skin reaction (HFSR), also known as palmar-plantar erythrodysesthesia or PPE, diarrhea, mucositis, weight loss, infection, and hypertension. Interestingly, most AEs occurred early in the treatment course, during cycles 1 and 2, and their incidence decreased over subsequent cycles of therapy. Further, the dosing of Regorafenib remained relatively stable after three cycles of treatment, and there was no evidence of cumulative toxicity. These data suggest that the incidence of drug-related AEs decreases over time, and that proactive AE management early on may help to decrease the incidence or severity of those AEs that occur during the course of treatment, thus enabling better treatment compliance and adherence to therapy (58). Therefore, a robust rationale may be made to start at a dose of 120 mg once daily for 3 of every 4 weeks and incorporate close monitoring in the initial 2 cycles followed by gradual tapering of monitoring. In addition, the accrual of performance status 0-1 patients only (and excluding PS=2 patients) will mitigate the risk of AEs.

We propose a non-randomized proof-of-concept phase II trial to evaluate Regorafenib for patients with metastatic progressive urothelial carcinoma following 1-3 prior chemotherapy regimens who still have an ECOG performance status 0-1. Given the lack of validated predictive biomarkers for the efficacy of Regorafenib, all patients will be enrolled. Additionally, the initial dose will be 120 mg daily since Regorafenib dose reductions are common in colorectal cancer and GIST patients (see data below). However, dose will be escalated to 160 mg daily from cycle 2 day 1 or later if no Regorafenib-related >grade 1 toxicities are seen in cycle 1. Moreover, close monitoring is incorporated especially during the first 2 cycles, which then gradually tapers (see schedule table below). However, given a disease with substantial unmet needs and the lack of any FDA approved salvage agents for this disease, the potential benefits provided by this strategy are expected to outweigh the risks.

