5.1.4 Selection of study population

General Guidelines

Eligible patients will be entered on study at the following institutions: the Kirklin Clinic, UAB, Birmingham, AL; Wayne State University Karmanos Cancer Institute, Detroit, MI; (UAB research nurse to be designated by [name], Director of UAB Oncology Clinical Trials, Clinical Studies Unit (CSU), UAB). All sites should call the Study Coordinator to verify agent availability. Following registration, patients should begin protocol treatment within 72 hours. Issues that would cause treatment delays should be discussed with the Principal Investigator. If a patient does not receive protocol therapy following registration, the patient's registration on the study may

be cancelled. The Study Coordinator should be notified of cancellations as soon as possible.

Registration Process

The Clinical Trials Network Monitoring Office (CTNMO) of the UAB Comprehensive Cancer Center (CCC) coordinates investigator-initiated clinical trials under Good Clinical Practice conditions at participating sites to achieve timely study subject enrolment. Once a study subject has been screened and deemed eligible for study entry by the participating site, a study-specific study subject eligibility checklist, a copy of the dated and signed consent form, and corresponding source documentation are faxed to the participating site study coordinator for eligibility verification. Subsequently, a study-specific number is assigned to the study subject and sent to the participating site. Finally, a Patient Registration Form is completed and faxed by the CTNMO site to the participating study coordinator. Queries regarding data accuracy are forwarded from the participating site coordinator to the CTNMO site for clarification or correction. Once the CTNMO site addresses queries, any corrected data forms or copies of corrected source documentation are faxed to the participating site study coordinator.

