8.3 Statistical and analytical plans

The primary endpoint of the study is the rate of progression free survival (PFS) at 6 months (PFS6). Given the poor prognosis of this patient population and data from other studies of salvage therapy, a PFS6 of $\geq 20\%$ is felt to be important for this regimen, while a PFS6 $< 5\%$ is felt to be of poor interest. The trial also enrolls patients who progress within 6 months of last cycle of prior chemotherapy to enhance the interpretability of outcomes, since such patients are unlikely biologically to be progression-free for 6 more months without active therapy that favorably impacts on tumor biology to extend PFS. SAS version 9.3 was used to calculate power. The justification for the proposed sample size is based on an exact test for a binomial proportion with a one-sided significance level of 5%. With 32 evaluable subjects,

we will have approximately 80% power (79.6%) to reject the null hypothesis that PFS6 is < 5% in favor of PFS6 \geq 20%. Given that 5-10% of patients may be inevaluable, up to 35 patients may be enrolled. If five or more patients remain progression-free at 6 months, this regimen will be considered to be of significant interest.

Chi-square or Fisher's exact test will be employed to determine univariate association of biomarker status with PFS6 and objective response. Descriptive statistics including frequencies and proportions will be calculated to summarize safety and toxicity outcomes. Specifically, the number of adverse events (AE) and serious adverse events (SAE) will be tabulated and summarized. Point estimates and exact binomial (Clopper-Pearson) confidence intervals (CI) will be calculated to estimate the incidence of AEs and SAEs. The precision of these estimates, i.e., width of the confidence interval, will depend on the estimated incidence of each outcome. The table below gives the exact 95% confidence intervals for a range of incidences, assuming 32 evaluable subjects.

Number of subjects experiencing event	Estimated Incidence	95% Exact CI for Incidence		Width of CI
		Lower Limit	Upper Limit	
1	0.031	0.001	0.162	0.161
2	0.062	0.008	0.208	0.200
4	0.125	0.035	0.290	0.255
8	0.250	0.115	0.434	0.319
16	0.500	0.319	0.681	0.362

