11.1 Ethical and legal conduct of the study

The procedures set out in this protocol, pertaining to the conduct, evaluation, and documentation of this study, are designed to ensure that the investigator abide by Good Clinical Practice (GCP) guidelines and under the guiding principles detailed in the Declaration of Helsinki. The study will also be carried out in keeping with applicable local law(s) and regulation(s).

Documented approval from appropriate IEC(s)/IRBs will be obtained for all participating centers before start of the study, according to GCP, local laws, regulations and organizations. When necessary, an extension, amendment or renewal of the EC/IRB approval must be obtained and also forwarded to Bayer.

Strict adherence to all specifications laid down in this protocol is required for all aspects of study conduct; the investigator may not modify or alter the procedures described in this protocol.

Modifications to the study protocol will not be implemented by the investigator without discussion and agreement by Bayer. However, the investigator may implement a deviation from, or a change of, the protocol to eliminate an immediate hazard(s) to the trial subjects

without prior IEC/IRB/Bayer approval/favorable opinion. As soon as possible, the implemented deviation or change, the reasons for it and if appropriate the proposed protocol amendment should be submitted to the IEC/IRB/head of medical institution. Any deviations from the protocol must be explained and documented by the investigator.

The Principal Investigator is responsible for the conduct of the clinical trial at the site in accordance with Title 21 of the Code of Federal Regulations and/or the Declaration of Helsinki. The Principal Investigator is responsible for personally overseeing the treatment of all study patients. The Principal Investigator must assure that all study site personnel, including sub-investigators and other study staff members, adhere to the study protocol and all FDA/GCP/NCI regulations and guidelines regarding clinical trials both during and after study completion.

The Principal Investigator at each institution or site will be responsible for assuring that all the required data will be collected and properly documented.

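### The inclusion criteria admit ECOG performance status 0 to 2, while the safety rationale says PS 2 patients are excluded; no other available text settles which range applies

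*Combined protocol and SAP*

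**What the plan says.** Section 5.1.1 opens with a binding statement: "Each patient must meet all of the following inclusion criteria to be enrolled in the study". One item in that list is "ECOG Performance status 0 - 2".

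Section 1.2 gives a narrower range twice. In arguing for a lower starting dose with close early monitoring, it adds a further protective measure: "the accrual of performance status 0-1 patients only (and excluding PS=2 patients) will mitigate the risk of AEs". The next paragraph, which describes the proposed trial, limits it to patients "who still have an ECOG performance status 0-1".

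Section 5.1.4 has the site's eligibility decision verified against "a study-specific study subject eligibility checklist" together with the consent form and source documents. The content of that checklist is not shown.

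**The concern.** The parenthesis in Section 1.2 names exactly the group that Section 5.1.1 admits. Because Section 1.2 gives the narrower range in two separate sentences, a single slip of the pen there is unlikely.

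Two things are at stake.

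- **Safety rationale.** Section 1.2 reports that dose reductions may be needed in up to 60-70% of patients who start at 160 mg. It then sets out a lower starting dose, close monitoring and the PS restriction as ways to reduce that burden, and concludes that the expected benefit outweighs the risk. If sites apply Section 5.1.1, one of those three elements is absent. An ethics committee or funder relying on Section 1.2 would believe that PS 2 patients are kept out.
- **Interpretation.** Section 1.1.1 treats PS as prognostic for progression-free and overall survival, and Section 8.3 uses it as an input to the nomogram for predicted PFS6. A reader of a single-arm PFS6 result needs to know which PS range was eligible.

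**Working it through.** This is a conflict of text, so the main check is to set the relevant places side by side and look for anything that resolves them.

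| Place | What it gives on PS at entry |
|---|---|
| 5.1.1 Inclusion criteria | 0 to 2, binding |
| 1.2 Rationale, safety argument | 0 to 1, PS 2 explicitly excluded |
| 1.2 Rationale, proposed population | 0 to 1 |
| Synopsis | no range |
| 4 Study design | no range |
| 5.1.2 Exclusion criteria | PS not mentioned |
| 5.2.1 Withdrawal | only deterioration to PS 4 on study |
| 7.1 Timing of Assessments | schedules PS assessment, no limit |
| 8.1 to 8.3 Statistics | no entry range; PS appears only as a nomogram input |
| 13 Amendments | headings without content |
| 14.2 Performance Status Criteria | defines the scale only |

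Three items cannot be counted either way. The trial schema has no readable content in the available copy. A margin comment at the end of the inclusion list says a definition is unchanged but names no criterion. A portion of text within the adverse event reporting part of Section 7.4.1 was not available; given its position, it is unlikely to bear on eligibility.

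No reading satisfies both sections. If Section 5.1.1 governs, the statement that PS 2 patients are excluded is false. If Section 1.2 governs, the inclusion criterion is too wide.

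**Does the conflict touch the design figures?** Section 8.3 states that "we will have approximately 80% power (79.6%) to reject the null hypothesis". The inputs, all from that section, are 32 evaluable patients, a null PFS6 of 5%, a target PFS6 of 20%, a one-sided exact binomial test at 5%, and success if five or more patients are progression-free at 6 months.

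- Power: P(X ≥ 5 | n = 32, p = 0.20) = 1 − Σ(k = 0 to 4) C(32, k) · 0.20^k · 0.80^(32−k) = 0.7956, which matches the stated 79.6%.
- Actual one-sided error: P(X ≥ 5 | n = 32, p = 0.05) = 0.0204, within 5%.
- A cut-off of four would give an error of 0.0738, above 5%, so five is the correct critical value.

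PS enters none of these expressions. Reconciling the two sections therefore leaves the stated sample size and power as they are.

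**The case against.** The best reply is that Section 5.1.1 is the operative list and Section 1.2 is background, so a site would in practice apply PS 0 to 2 and there is no ambiguity in conduct. This has some force: eligibility decisions normally follow the numbered criteria. But the protocol does not rank its sections, and Section 11.1 demands strict adherence to all of its specifications. Even if Section 5.1.1 prevails, the safety statement in Section 1.2 is then wrong as written and still needs correction.

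A second reply is that other protections remain whatever the PS: the lowered starting dose with conditional escalation, the dose-modification tables, the liver and blood pressure checks, weekly committee review of adverse reactions, the minimum life expectancy and organ-function limits at entry, and the investigator's discretion to exclude an unsuitable patient. This stands, and it limits the practical consequence. In Section 1.2 the PS restriction is an addition to the dose and monitoring arguments, not the whole of them. None of these protections makes the exclusion statement true.

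A third point is timing. The protocol version is dated December 2018, the cover February 2020, and Section 8.1 plans 6 to 12 months of accrual. The documents do not give enrolment status. If accrual is over, an amendment cannot change who is treated. That affects the form of the remedy, not the existence of the conflict.

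**Conclusion.** The concern holds. The protocol gives two incompatible PS ranges for the same population, and one of them is offered as a safety measure. It should be corrected, but it is not a flaw in the primary test.

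Its size is bounded but not known. At most 35 patients may be enrolled, and with no expected PS 2 share in the documents the number affected cannot be given. No stated statistical figure changes. Any estimate of an effect on power would need an assumed PS 2 share and an assumed PFS6 in those patients, neither of which the plan supplies, and the point does not depend on one.

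The conclusion rests on the text that could be read. A legible schema or the eligibility checklist might show which range was applied in practice, but it would not remove the contradiction between Sections 1.2 and 5.1.1.

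**What to change.** Amend the protocol so that a single PS range appears in both Section 5.1.1 and Section 1.2, and check that the eligibility checklist matches it. This review takes no position on which range is correct.

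- If PS 2 remains eligible: delete the claim in Section 1.2 that such patients are excluded, align the second PS 0-1 sentence there, and have the sponsor justify the risk mitigation for PS 2 patients.
- If PS 2 is to be excluded: change the criterion in Section 5.1.1.
- If enrolment has closed: state in the study report the PS range actually enrolled and correct the rationale to match. Section 7.1 already schedules PS at baseline, so no new data are needed.

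The drafting is small, but an amendment carries procedural steps. Section 11.1 says that "Modifications to the study protocol will not be implemented by the investigator without discussion and agreement by Bayer" and that, when necessary, "an extension, amendment or renewal of the EC/IRB approval must be obtained and also forwarded to Bayer". Section 11.2 calls for a revised consent form if the amendment alters what patients need to be told. The sample size, test and decision rule stay as they are.
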